2.2.1. Scientific Rationale for Study Design

Ruxolitinib 1.5% cream BID, which was shown to be safe and effective in Studies INCB 18424-303 and INCB 18424-304 and is the approved regimen in the US, will be assessed for safety and efficacy in this double-blind, multicenter, global study with 2 distinct VC periods (VC and VCE) and the option of an open-label escape arm. In the absence of a recommended third-line topical drug in Europe, the comparator in this study will be vehicle cream. Participants will be randomized 2:1 to the ruxolitinib 1.5% cream BID or vehicle cream BID group for the first 8 weeks of study. Coprimary and a key secondary efficacy endpoints will be assessed at Week 8, consistent with the previous Phase 3 studies. After completing 8 weeks of continuous treatment, all eligible participants with an adequate response, defined as achieving at least EASI50 from baseline, will continue on their blinded treatment allocation and will be evaluated during an additional 16-week VCE period for durability of response. Participants will be eligible to enter the ruxolitinib 1.5% cream open-label escape arm if EASI50 is not achieved at Week 8 or if an EASI50 response from baseline is lost during the VCE period.

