4. STUDY DESIGN

4.1. Overall Design

This is a Phase 3b, multicenter, randomized, double-blind, VC study with an extension period in adult (aged ≥ 18 years) participants with moderate AD who had an inadequate response to, or are intolerant to, or contraindicated to TCSs and TCIs (see [Figure 1](#)). The study will be conducted at approximately 100 sites in North America, Asia-Pacific, and Europe.

For participants who meet all study inclusion criteria and none of the exclusion criteria, study cream will be assigned at the Day 1/baseline visit. Approximately 225 participants will be randomized 2:1 to blinded treatment with ruxolitinib 1.5% cream BID or vehicle cream BID, with stratification by baseline EASI score (< 16 or ≥ 16) and geographic region (ROW or Europe).

During the 8-week VC period, participants will apply study cream BID to all areas identified for treatment at the Day 1/baseline visit even if the AD begins to improve and lesions decrease in size. If there are new areas to be treated (including expansion of existing areas or development of new areas), after consultation with the investigator, study cream should be applied to these areas in addition to the areas identified at the baseline visit (up to a maximum total of 20% BSA) for the remainder of the VC period. A study staff representative or designee will contact the participant at minimum 1 week prior to each clinic visit during the VC period to discuss eDiary compliance.

Efficacy will be evaluated during the VC period, including the proportion of participants achieving EASI75 and IGA-TS (coprimary endpoints), and ITCH4 at Week 8 as well as ITCH4 at Day 7, Day 3, and Day 2 (key secondary endpoints).

After completing 8 weeks of continuous treatment, all eligible participants with an adequate response, defined as achieving at least EASI50 from baseline, will continue blinded treatment allocation and will be evaluated during an additional 16-week VCE period for durability of response. Participants will be eligible to enter the ruxolitinib 1.5% cream open-label escape arm if EASI50 is not achieved at Week 8 or if an EASI50 response from baseline is lost during the VCE period (Note: $< \text{EASI50}$ must be observed at 2 consecutive visits, one of which can be an unscheduled visit, at least 1 week apart.)

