If there are new areas to be treated, including expansion of existing areas or development of new areas, after consultation with the investigator, study cream should be applied to these areas in addition to the areas identified at the baseline visit (up to a maximum total of 20% BSA) for the remainder of the VC period, and the percentage of BSA to be treated will be recalculated and increased accordingly. This new estimate will be entered into the IRT system to calculate the number of tubes of study cream to be dispensed. During the VC period, participants whose additional new areas to be treated in addition to the areas identified at the baseline visit exceed 20% BSA will be discontinued from study treatment and complete the ET visit.

The VCE period starts at the Week 8 visit and completes at the Week 24 visit, with the final possible application being the evening application on the day before the Week 24 visit. During the VCE period, only areas with active disease should be treated.

After completing 8 weeks of continuous treatment, all eligible participants with an adequate response, defined as achieving at least EASI50 from baseline, will continue their blinded treatment allocation and will be evaluated during an additional 16-week VCE period for durability of response. Participants will be eligible to enter the ruxolitinib 1.5% cream open-label escape arm if EASI50 is not achieved at Week 8 or if an EASI50 response from baseline is lost during the VCE period. (Note: < EASI50 must be observed at 2 consecutive visits, one of which can be an unscheduled visit, at least 1 week apart.)

The start and end dates of treatment applications will be captured by the participant. Once the lesions clear (IGA score of 0), participants should continue to apply study cream for an additional 3 days to the areas of the body where lesions were last present before discontinuing treatment. Following clearance, if a lesion recurs, treatment should be resumed at the first sign of recurrence.

At any time during the VCE period, if a participant's total AD-affected area exceeds 20% BSA, the participant will be discontinued from study treatment and complete the ET visit.

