**Figure 1: Study Design Schema**

### 3.1. Randomization

In the VC period, the interactive response technology system will assign approximately 225 participants in a 2:1 ratio to ruxolitinib 1.5% cream BID or vehicle cream BID. Additionally, participants will be stratified by baseline EASI score ( $< 16$  or  $\geq 16$ ) and geographic region (ROW vs Europe).

All eligible participants with an adequate response, defined as achieving at least EASI50 from baseline, will continue into the 16-week VCE period with the same treatment regimen. Participants who did not achieve EASI50 at Week 8 or for whom an EASI50 response from baseline is lost during the VCE period will be eligible to enter the ruxolitinib 1.5% cream open-label escape arm.

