### 7.5.2.3. Time-to-Event Efficacy Endpoints

The following time-to-event endpoints will be analyzed:

- Time to achieve ITCH4 during the VC period.
- Time to achieve ITCH2 during the VC period.
- Time to open-label escape arm  
(defined as not achieving 50% improvement in EASI score from baseline at 2 consecutive visits at least 1 week apart, with the earliest possible time to enter escape arm being at the Week 8 visit)
- Time to concurrently meeting all of the following criteria: IGA score  $\geq 3$ , EASI score  $\geq 16$ , Itch NRS score  $\geq 4$ , BSA  $\geq 10\%$ , and DLQI score  $> 10$ .

For the time to open-label escape arm analysis, the start time will be set to the Week 8 date and only the participants who entered VCE period will be considered as at risk. Participants who were incorrectly assigned to escape arm without meeting the criteria will be censored at the date of their first dose in the escape arm.

A log-rank test stratified by randomization stratification factors will be used for between treatment group comparisons. The hazard ratio and its 95% CI will be estimated based on the stratified Cox regression model using Efron's method accounting for ties. Kaplan-Meier curves will be presented by treatment group. The number of participants, number of events, and number of censoring will be summarized by treatment group. The Kaplan-Meier estimate of median time will be presented with its 95% CI. The 95% CI will be calculated using the method by Brookmeyer and Crowley (1982).

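### The escape-arm criterion is stated as one missed EASI50 in some sections and two consecutive misses in others, so the handling and analysis of a participant who first misses EASI50 at Week 8 are not defined

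*SAP*

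**What the plan says.** **One-visit wording.** Protocol 2.2.1 reads: "Participants will be eligible to enter the ruxolitinib 1.5% cream open-label escape arm if EASI50 is not achieved at Week 8", with loss of EASI50 during the extension as the other route. The Protocol Summary (Treatment Groups and Duration) carries the same rule. SAP 3.1 gives escape eligibility to "Participants who did not achieve EASI50 at Week 8 or for whom an EASI50 response from baseline is lost during the VCE period". None of the three asks for confirmation.

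**Two-visit wording.** Protocol 4.1 attaches a note that a result below EASI50 "must be observed at 2 consecutive visits, one of which can be an unscheduled visit, at least 1 week apart". The same note is in Protocol 6.1, SAP 1 and SAP 3. The time-to-escape endpoint follows it: SAP 7.5.2.3 has the event "defined as not achieving 50% improvement in EASI score from baseline at 2 consecutive visits at least 1 week apart", as do Protocol Table 5 and SAP Table 1.

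**Who stays on blinded cream.** Protocol 4.1 says that "all eligible participants with an adequate response, defined as achieving at least EASI50 from baseline, will continue blinded treatment allocation"; Protocol 6.1 is equivalent.

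**Analysis.** SAP 7.5.2.3 starts the clock at the Week 8 date, takes those who entered the extension as the risk set, and allows escape from the Week 8 visit at the earliest. On switches outside the rule it says: "Participants who were incorrectly assigned to escape arm without meeting the criteria will be censored at the date of their first dose" in that arm.

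**The concern.** An open-label switch is a treatment decision, and for some participants the answer depends on which section is followed. Those concerned had EASI50 at Week 4 and missed it at Week 8. They may switch at once under one set of passages and not yet under the other. Continued blinded treatment is written only for those who achieved EASI50, so their cream until confirmation is not specified.

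The analysis inherits the problem. The event is built on EASI, and a single-visit switcher leaves blinded treatment because of EASI. If that person is censored at the switch, the censoring is tied to the outcome, contrary to what the Kaplan-Meier, log-rank and Cox methods assume. The estimate of time to escape would then tend to look too favourable in whichever arm has more such switches.

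The same ambiguity affects who enters the escape-arm IGA-TS and EASI75 summaries, which are limited to participants who entered at Week 8 (SAP 7.5.2 and Appendix A). It also affects who belongs to the VCE primary population, which requires a dose in the double-blind extension (SAP 5.3.5).

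**Working it through.** The plan states no figure on this point, so there is none to reproduce. The check sets the rules side by side.

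**Step 1. Week 4 and Week 8 patterns against each rule.** A Week 4 miss is taken as able to serve as the first of two; SAP 7.5.2.3 supports this by allowing entry at the Week 8 visit.

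| EASI50 at Week 4 | EASI50 at Week 8 | Continue blinded? | Escape at Week 8, one-visit text | Escape at Week 8, two-visit text |
|---|---|---|---|---|
| met | met | yes | no | no |
| not met | met | yes | no | no |
| not met | not met | no | yes | yes |
| met | not met | no | yes | **no** |

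Only the last row is in conflict. Participants who miss at both visits satisfy both versions. A missing Week 4 EASI is unclear: misses at Weeks 2 and 8 might count as consecutive attended visits.

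**Step 2. What the SAP does with the last row if the participant switches at Week 8.** Escape entry is handled through the IRT at scheduled or unscheduled visits (Protocol 8.1.3), and cream is applied on site at Week 8 unless IGA is 0 (Protocol Table 3). The first escape dose therefore falls on or near the Week 8 date, which is the time origin.

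- *Criteria read as the two-visit rule:* no event has occurred, the switch counts as incorrect, and the participant is censored at about time zero. They add almost nothing to the risk set. Whether the miss would have been confirmed on the assigned cream can no longer be seen.
- *Criteria read as the one-visit text:* the switch is correct, so the censoring sentence does not apply. The two-visit event has not occurred either. The SAP gives no handling.

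**Step 3. How many could be in that row.** The documents give no EASI50 rates, so this is an illustration on assumptions.

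- Planned arms: 225 at 2:1 gives 150 ruxolitinib and 75 vehicle.
- Protocol Table 9 assumes EASI75 in 70% and 15%. Anyone below EASI50 is also below EASI75, so on those rates Week 8 misses are at most 150 × 0.30 = 45 and 75 × 0.85 = 63.75, about 64.
- Assume that a fraction f of these, 5% to 30%, had met EASI50 at Week 4.
- Vehicle: 63.75 × 0.05 = 3.2 to 63.75 × 0.30 = 19.1, about 3 to 19.
- Ruxolitinib: 45 × 0.05 = 2.25 to 45 × 0.30 = 13.5, about 2 to 14.

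These are ceilings for each f, because participants with 50% to 74% improvement sit inside the 45 and 64 but did not miss EASI50. They count people exposed to the ambiguity, not the effect on the estimate.

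**Step 4. Direction.** As shares of each arm the ceilings are 0.85f on vehicle and 0.30f on ruxolitinib, so with equal f vehicle has more. Equal f is an assumption: with f = 5% on vehicle and 30% on ruxolitinib the shares are 4.25% and 9.0%, and the order reverses. Hence probably, and no more, for the vehicle arm.

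**The case against.** The best reply is that this is an omission and not a conflict. The operative sections (Protocol 4.1 and 6.1, SAP 1 and 3) and every endpoint definition carry the two-visit rule; the short versions are a summary, a rationale and a randomization paragraph. The IRT Manual, which was not available, may enforce one rule. That is plausible, but no passage says that the note governs, and SAP 3 and SAP 3.1 differ within one document.

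Three stronger readings are tempting, and the documents do not support them.

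- *A reader might infer that these participants fall outside every rule.* They do not. Protocol Table 3 footnote d and Protocol 8.2.2 tie extension entry to BSA up to 20%, and Protocol 8.2.3 accepts any IGA at Week 8 and has those with IGA of 1 or more use cream. An unscheduled visit at least a week later can settle the case. What is missing is whether the cream is blinded or open-label meanwhile.
- *A reader might infer that the SAP certainly censors them as wrongly assigned.* That holds only under the first reading in Step 2.
- *A reader might infer that escape-free survival at Week 8 is overstated by the share of single-visit switchers.* It is not. Under the planned two-visit event they have had no event at Week 8; counting them there substitutes a different endpoint. Bias from informative censoring would appear after Week 8, and its size depends on how many misses would have been confirmed.

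It is also true that censoring counts are reported by arm and that individual escape times and deviations are listed (SAP 7.5.2.3 and Appendix A). That makes the problem visible but does not settle the analysis.

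**Conclusion.** The inconsistency is in current text and needs resolving. It is narrow: it concerns participants whose first result below EASI50 is at Week 8, and it lasts until confirmation. The statistical consequence depends on how the criteria in SAP 7.5.2.3 are read, and neither reading is satisfactory: one gives informative censoring at about time zero, the other leaves the participant without a defined status.

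The size of the effect on the time-to-escape analysis cannot be derived from the documents. The counts in Step 3 rest on the Table 9 design rates and an assumed Week 4 response, and they bound exposure only. The endpoint is secondary and outside the fixed testing sequence (Protocol 10.3, SAP 3.2), and the Week 8 coprimary results are not affected. The change is worth making because it is cheap, and because the handling of a participant should not turn on which section is consulted.

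**What to change.** 1. Reconcile the Protocol Summary, Protocol 2.2.1, 4.1 and 6.1, and SAP 1, 3 and 3.1 with the endpoint definition in Protocol Table 5, SAP Table 1 and SAP 7.5.2.3, so that one escape criterion is stated. Include the handling of a participant who first misses EASI50 at Week 8, and whether cream is blinded or open-label until the matter is settled. This review does not say which rule is right.
2. Align the event and censoring definitions in SAP 7.5.2.3 with the reconciled rule, and name the criteria to which the censoring sentence refers.
3. If the two-visit definition is kept for the main analysis, prespecify a sensitivity analysis. Count entry to the escape arm with less than 50% EASI improvement at the entry visit as an event on that date, and censor as incorrectly assigned only those at or above EASI50 at entry. This should not replace the main analysis: a single miss would then be an event at a site that switches early and not at one that waits, and the result would depart from Protocol Table 5.

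The cost is a wording clarification in both documents and one extra analysis. EASI is already collected at every scheduled visit. The SAP change should be made before the primary database lock, after which the sponsor is unblinded (Protocol 10.6).

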#### **7.5.2.4. Analysis of Desensitization and Rebound in the VCE DB Period**

The following categorical parameters will be summarized by treatment to assess rebound upon treatment cessation:

- Proportion of participants who experience a relapse after study treatment discontinuation. (ie, proportion of participants among EASI75 responders who are on study treatment at Week 24 who meet relapse criteria [loss of EASI50 from baseline] at the safety follow-up visit)

[figure not shown]
The following endpoints will be summarized by treatment and visit to assess desensitization upon treatment cessation:

[figure not shown]
[figure not shown]
- Proportion of time off study treatment due to lesion clearance during the VCE period by visit
- Proportion of time on study treatment during the VCE period by visit

Time to first re-treatment is defined as the interval between the first interruption due to lesion clearance starting from Week 8 to the end of the VCE period and the time of starting the re-treatment. This analysis will be performed in the VCE re-treatment evaluable population as defined in Section 5.3.7. The Kaplan-Meier estimate of median time to first re-treatment will be presented with its 95% CI. The 95% CI will be calculated using the method by Brookmeyer and Crowley (1982).

### **7.6. Analysis of Exploratory Efficacy Parameters**

#### **7.6.1. Exploratory Efficacy Analysis**

## **9. SAFETY AND TOLERABILITY**

[Appendix A](#) provides a list of planned tables, figures, and listings. Sample data displays are included in a separate document.

### **9.1. General Considerations**

The analyses in this section will be provided for the safety population in the VC period, VCE primary population as well as VCE escape population in the VCE period. Cumulative TEAEs across the treatment periods (VC and VCE periods) will be summarized. Summary tables may be replaced with listings when appropriate. For instance, an AE frequency table may be replaced with a listing if it only contains a few unique PTs reported on relatively few participants.

### **9.2. Adverse Events**

#### **9.2.1. Adverse Event Definitions**

A TEAE is any AE either reported for the first time or worsening of a pre-existing event after first application of study drug and within 30 days after the last dose of study drug. For participants who were initially on vehicle cream and crossed over to the ruxolitinib cream escape arm, the first application date is period specific, and the end date is 30 days after the last application date in this period, or the first application date in the next period, whichever comes first. Analysis of AEs (as discussed below) will be limited to TEAEs, but data listings will include all AEs regardless of their timing in relation to study drug administration.

Adverse events will be tabulated by MedDRA PT and SOC. Severity of AEs will be graded using the National Cancer Institute CTCAE. The CTCAE v5.0 (Grade 1 to 5) is used for this study. The CTCAE reporting guidelines and grading details are available on the Cancer Therapy Evaluation Program website.

The subset of AEs considered by the investigator to be related to study drug will be considered to be treatment-related AEs. If the investigator does not specify the relationship of the AE to study drug, the AE will be considered treatment-related. The incidence of AEs and treatment-related AEs will be tabulated. In addition, serious AEs will also be tabulated.

Any missing onset date, causality, or severity must be queried for resolution. Unresolved missing causality and severity will be handled according to the following rules:

- An unresolved missing causality will be considered treatment-related.
- An unresolved missing severity will be identified as an unknown severity.

For purposes of analysis, all AEs will be considered TEAEs unless the AE can unequivocally be defined as not treatment-emergent.

Application site reactions are AEs that occur at the site of drug application. A summary of ASRs will be provided. Exposure-adjusted summaries will be provided for the safety population, including cumulative TEAEs and cumulative ASRs.

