Furthermore, investigators should consider alternative treatment options, such as systemic therapies, at or after completing the Week 8 visit, if any participant meets all of the following criteria (Note: prior to initiation, the investigator should discontinue study cream and the therapy escalation will be recorded in the eCRF):

- IGA score ≥ 3
- EASI score ≥ 16
- Itch NRS score ≥ 4
- BSA $\geq 10\%$

During the VCE period, participants (including those in the escape arm) will have study visits every 4 weeks for up to 24 weeks total. At each of these visits, including Week 8, the participant's AD lesions will be evaluated by the investigator to determine whether the

participant requires continuation of treatment or should (re)enter an observation/no treatment period. If the IGA score is ≥ 1 , the participant will start or continue study cream BID. If the IGA score is 0 (clear), the participant will (re)enter an observation/no treatment period. Note: Participants should stop treatment application 3 days after the lesions have cleared.

Furthermore, during the VCE period (ie, starting at the Week 8 visit), participants will self-evaluate their AD symptoms between study visits and will treat areas of the skin (not to exceed 20% BSA) with active AD lesions only. If AD lesions clear at any time before the Week 24 visit, participants will stop treatment applications 3 days after the lesions have cleared and record the dates of these events in their eDiary. Participants who were in an observation/no treatment period will restart treatment at home at the first sign of recurrence and record the date of the new treatment. All treatment will be captured in the clinical database with the beginning and end dates as confirmed by the participant in the eDiary. A study staff representative or designee will contact the participant in between regularly scheduled clinic visits (eg, Weeks 10, 14, 18, and 22) to discuss eDiary compliance and to confirm the start and end date of treatment as applicable.

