8.3.1. Adverse Events

Adverse events will be monitored from the time the participant signs the ICF until at least 30 days after the last application of study cream. Adverse events for enrolled participants that begin or worsen after informed consent should be recorded on the Adverse Events Form in the eCRF regardless of the assumption of a causal relationship with the study cream. Conditions that were already present at the time of informed consent should be recorded on the Medical History Form in the eCRF. Adverse events (including laboratory abnormalities that constitute AEs)

should be described using a diagnosis whenever possible rather than by individual underlying signs and symptoms.

Adverse events will be reported by the participant (or, when appropriate, by a caregiver or surrogate). The investigator and any qualified designees are responsible for detecting, documenting, and recording events that meet the definition of an AE or SAE and remain responsible for following up on AEs that are serious, that are considered related to the study cream/procedures, or that caused the participant to discontinue the study cream. Care will be taken not to introduce bias when detecting AEs and/or SAEs. Open-ended and nonleading verbal questioning of the participant, such as "How are you feeling?," is the preferred method to inquire about AE occurrences. Adverse events may also be detected when they are volunteered by the participant during the screening process or between visits or through physical examinations, laboratory tests, or other assessments. The definition, reporting, and recording requirements for AEs are described in Section 9.

All SAEs will be reported to the sponsor or designee by the investigator immediately without undue delay and not later than 24 hours of obtaining knowledge of the events. The investigator will also submit any updated SAE data to the sponsor immediately without undue delay and not later than 24 hours of obtaining knowledge of the update.

After the initial AE/SAE report, the investigator is required to proactively follow each participant at subsequent visits/contacts. All SAEs will be followed until resolution, stabilization, the event is otherwise explained, or the participant is lost to follow-up (see Section 7.3).

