8.9. Follow-Up

8.9.1. Safety Follow-Up

The safety follow-up period is the interval between the Week 24/EOT or ET visit and the scheduled follow-up visit, which should occur 30 days after the Week 24/EOT or ET visit, with the following 2 exceptions:

- The follow-up visit should occur at the Week 24/EOT visit for participants who have been in an observation/no treatment period with an IGA score of 0 (clear) from Week 20 or earlier until Week 24.
- The follow-up visit should occur 30 days after the last application of study cream if the Week 24/EOT or ET visit was not performed.

New AE and SAEs must be reported up until 30 days after the last application of study cream; ongoing AEs and SAEs must be followed up until toxicities resolve, return to baseline, or are deemed irreversible, whichever is longer. Reasonable efforts should be made to have the participant return for the follow-up visit and report any AEs that may occur during this period.

9. ADVERSE EVENTS: DEFINITIONS AND PROCEDURES FOR RECORDING, EVALUATING, FOLLOW-UP, AND REPORTING

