10.4.3. Safety Analyses

Safety analyses will be conducted for the safety population.

A TEAE is any AE either reported for the first time or worsening of a pre-existing event after first application of study cream and no later than 30 days after the Week 24 or ET visit. Analysis of AEs will be limited to TEAEs, but data listings will include all AEs regardless of their timing in relation to study cream administration. Adverse events will be tabulated by the MedDRA preferred term and system organ class. Severity of AEs will be based on the National Cancer Institute CTCAE v5.0 using Grades 1 through 5.

The subset of AEs considered by the investigator to have a causal relationship to study cream will be considered treatment-related AEs. If the investigator does not specify the relationship of the AE to study cream, then the AE will be considered treatment-related. The incidence of AEs and treatment-related AEs will be tabulated.

The clinical laboratory data will be analyzed using summary statistics; no formal treatment group comparisons are planned. Laboratory test values outside the normal range will be assessed for severity based on the normal ranges for the clinical reference laboratory. The incidence of abnormal laboratory values and shift tables relative to baseline will be tabulated. Descriptive statistics and mean change from baseline will be determined for vital signs (blood pressure, pulse, respiratory rate, and body temperature) at each assessment time.

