### 11.1. Changes to Protocol-Defined Analyses

All endpoints in Section 2.2 have been rephrased from the Protocol in a manner that is consistent with estimand guidance. The rephrasing is a change in presentation only and does not alter the interpretation or intended analyses of these endpoints from the Protocol.

The definition of VCE primary population and VCE escape population in Sections 5.3.5 and 5.3.6 has been modified in a more accurate language.

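### SAP 9.2.1 ends the TEAE window 30 days after the last dose, the protocol 30 days after Week 24 or ET; the undeclared change takes late off-cream AEs out of the TEAE tables

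*SAP*

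**What the plan says.** **Two definitions of the window.** Protocol Section 10.4.3 defines a TEAE as an event that is new or worsens "after first application of study cream and no later than 30 days after the Week 24 or ET visit". SAP Section 9.2.1 defines it as one that is new or worsens "after first application of study drug and within 30 days after the last dose of study drug". For vehicle participants who move to the escape arm, the SAP also cuts the window at the first application of the next period.

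**Declared changes.** SAP Section 11.1 lists a rephrasing of the endpoints and one further item: "The definition of VCE primary population and VCE escape population in Sections 5.3.5 and 5.3.6 has been modified in a more accurate language". The TEAE window is not mentioned.

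**As-needed dosing.** In the extension, Protocol Section 4.1 says: "If the IGA score is 0 (clear), the participant will (re)enter an observation/no treatment period". Cream is stopped 3 days after lesions clear and restarted at recurrence. Section 6.1 puts the latest application at Week 24, with "the final possible application being the evening application on the day before the Week 24 visit". Protocol Table 4 keeps AE assessment at Weeks 12, 16, 20 and 24 and at safety follow-up, on or off cream.

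**AE collection.** Protocol Section 8.3.1 monitors AEs "until at least 30 days after the last application of study cream". Section 8.9.1 says: "New AE and SAEs must be reported up until 30 days after the last application of study cream". The same section merges two visits for some participants: "The follow-up visit should occur at the Week 24/EOT visit for participants who have been in an observation/no treatment period", provided they have been clear (IGA 0) since Week 20 or earlier.

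**The concern.** With continuous dosing the two rules would almost coincide. With as-needed dosing they do not. Under the SAP rule the window closes 30 days after a participant's final application, even if that participant remains in the randomised extension and attends later visits at which AEs are assessed. How long a participant can contribute a TEAE then depends on how well the disease has cleared, which is an outcome after randomisation.

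SAP Section 9.2.1 limits the AE analyses to TEAEs, and Section 9.2.2 reports number and percentage of participants. A shorter window can only lower such a percentage. The categories of interest in Section 9.2.2 include malignancies, cardiovascular events and thromboembolic events, for which an onset after cream has stopped would still be of interest. Because the change is not declared, a reader of the study report would assume that the tables follow the protocol definition.

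**Working it through.** The plan gives no figure for the length of the window, so the check is a day count.

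**Inputs.** Nominal days are Week 8 = Day 57, Week 12 = Day 85, Week 16 = Day 113, Week 20 = Day 141 and Week 24 = Day 169 (SAP Section 4.1.2 numbering; visit windows ignored). L is the day of the final application, at most Day 168.

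**Formulas**, for a participant who reaches Week 24:
- SAP window end = L + 30.
- Protocol window end = 169 + 30 = Day 199.
- Nominal gap = 199 − (L + 30) = 169 − L, which is the number of days from the last application to the Week 24 visit.
- Observed gap when follow-up is merged into Week 24 = 169 − (L + 30) = 139 − L, or zero if negative.

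| Final application | SAP window ends | Nominal gap (to Day 199) | Gap to Week 24 visit | Scheduled visits from Week 12 to Week 24 outside the SAP window |
|---|---|---|---|---|
| Day 60 (3 days after Week 8) | Day 90 | 109 | 79 | Weeks 16, 20, 24 |
| Day 85 | Day 115 | 84 | 54 | Weeks 20, 24 |
| Day 113 | Day 143 | 56 | 26 | Week 24 |
| Day 141 | Day 171 | 28 | 0 | none |
| Day 168 | Day 198 | 1 | 0 | none |

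The gap to the Week 24 visit is the relevant one for participants clear and off cream since Week 20 or earlier, because they have no separate follow-up visit. Those whose final application is after Week 20 do have a follow-up visit; for them the nominal gap applies, from 169 − 142 = 27 days down to 1 day.

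**Which tables are affected** (SAP Appendix A):
- Crude tables for the double-blind (DB) part of the vehicle-controlled extension (VCE), on the VCE primary population: affected, and they compare arms. SAP Section 5.3.5 requires at least one application in that period, so the Day 60 row is close to the largest case.
- Crude Baseline-to-Week-24 tables: affected, but by title they cover only participants on ruxolitinib throughout, so they make no comparison with vehicle.
- Exposure-adjusted Baseline-to-Week-24 tables: the SAP does not state the denominator. Treatment duration in SAP Section 6.4 ends at the last application. If that is used, numerator and denominator are both cut, which partly offsets the loss.

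**Direction by arm.** No rate of IGA 0 or of sustained clearance is given. The nearest figure is the planning IGA-TS rate at Week 8, 60% vs 10% (Protocol Table 9), which with 2:1 allocation of 225 is 150 × 0.60 = 90 vs 75 × 0.10 = 7.5 participants. Assume that the same share f of these clears and stays off cream in each arm:

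| f (assumed) | Ruxolitinib, of 150 | Vehicle, of 75 |
|---|---|---|
| 10% | 9 (6%) | 0.75 (1%) |
| 25% | 22.5 (15%) | 1.9 (2.5%) |
| 50% | 45 (30%) | 3.75 (5%) |

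As a percentage of those randomised, the order reverses only if f on vehicle exceeds 60/10 = 6 times f on ruxolitinib. The VCE DB tables use a different denominator, those who entered the extension and applied cream, so this ratio does not carry over to them.

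**The case against.** The strongest defence is that the SAP agrees with the protocol's own collection rule. Section 8.9.1 requires new AEs to be reported until 30 days after the last application, so 10.4.3 is arguably the outlier. This stands in part: the protocol is not consistent with itself, and a SAP edit alone would leave that open. It does not remove the problem. Section 8.3.1 sets a minimum rather than a limit, Table 4 schedules AE assessment at every extension visit, and the SAP departs from the protocol's TEAE definition without saying so.

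Three further points limit the scope, and all stand:
- An AE in an off-cream gap that is followed by re-treatment stays inside the SAP window. Only AEs starting more than 30 days after the final application are lost.
- Excluded AEs remain in the listings, which keep all AEs. The SAP's default of treating doubtful AEs as treatment-emergent does not bring back those with known dates outside the window.
- A participant clear at Week 8 who never applies cream again is not in the VCE primary population under either window.

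A reader might also count to Day 199 and conclude that more than half of follow-up is lost (109 of 199 days for a last application on Day 60). The documents do not support that. Such a participant, if clear throughout, has follow-up merged into Week 24, so the observed loss is 79 of 169 days, or 47%.

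**Conclusion.** The two documents define the TEAE window differently, the change is undeclared, and with as-needed dosing it matters. Window length depends on response, and AEs starting more than 30 days after the final application are left out of the TEAE tables. For participants clear since Week 20 or earlier the observed loss is about 79 days (last application Day 60), 26 days (Day 113) or none (Day 141). Against the protocol's nominal Day 199 the gaps are 109, 56 and 28 days. These figures rest on nominal visit days. The crude between-arm effect is confined to the VCE DB tables.

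A reader might infer that the SAP rule makes ruxolitinib look safer than vehicle. The planning rates make a larger loss on ruxolitinib plausible, but the documents do not show it. IGA-TS includes IGA 1, at which cream continues, and no rate of sustained clearance is given. Vehicle participants who escape have their window cut for a response-related reason as well. The net bias between arms is therefore unknown.

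**What to change.** - In SAP Section 9.2.1, use the window of Protocol Section 10.4.3 for the main TEAE tables, keeping the existing cut at the first escape application.
- Show the version ending 30 days after the last application as a supplementary on-treatment display.
- State the person-time for the exposure-adjusted rates and match it to each window.
- If the sponsor prefers the last-dose window for the main tables, declare it in SAP Section 11.1 and add the AE summary under the protocol window as a sensitivity table.
- Reconcile the AE reporting periods in Protocol Sections 8.3.1 and 8.9.1 with Section 10.4.3, so that the data behind the chosen window are clearly required.

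**Cost.** SAP wording, some additional tables and a protocol clarification. AEs are already assessed at the extension visits. There are two downsides: some AEs arising off cream will count as treatment-emergent, and person-time based on follow-up adds off-cream days to the denominator, which could lower the adjusted rates. Showing both windows makes each effect visible.
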